4.3 Definition of end of the study

The study will end when the treatment period, safety follow-up, disease follow-up and survival follow-up have completed for all patients as described in [Section 7.1](#).

Completion of the survival follow-up period will occur once a minimum of 80% of patients in the Phase II stage have died, have been lost to follow-up, or have been followed for survival for minimum 12 months after the first dose of study treatment, see [Section 7.1](#).

The disease and survival follow-up evaluations might not be completed in case Haihe decides to stop enrollment prematurely. In such cases, end of study will be upon the Study Evaluation Completion (SEC) or the last patient treated, including the completion of the safety follow-up period.

See [Section 10.5](#) Statistical Methods and Data Analysis for details of timing of the primary analysis and final reporting of data.

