Based on the safety data at 6 dose levels, HH2710 was well tolerated from 25 mg BID to 400 mg QD. However, 1 of 4 patients at 800 mg dose cohort experienced DLT (Grade 3 Acneiform rash). 3 of 26 patients developed Grade 1-2 eye toxicity, 2 patients were from the 600mg dose group,

and 1 from 800mg dose. Since the drug-related factor may have contributed, we have de-escalated to 300mg QD dose. And further dosing frequency and dose level may be adjusted based on available safety and PK data.

Part B (Additional BID dose escalation cohorts):

In order to determine the RP2D, additional BID dosing cohorts may also be evaluated based on available clinical data using BOPIN design starting from 200mg BID dose and the total sample size in Part B is up to approximately 18 subjects. After the escalation is completed, select the MTD based on the isotonic regression as specified in [64]. Specifically, select the MTD for which the isotonic estimate of the toxicity rate is closest to the target toxicity rate. If there are ties, select the higher dose level when the isotonic estimate is lower than the target toxicity rate and select the lower dose level when the isotonic estimate is greater than or equal to the target toxicity rate.

Dose expansion stage:

Additional up to 15 patients per cohort may be included in order to further explore the safety, PK and anti-tumor activities among biomarker-selected patients. The dose for provisional cohort of expansion phase will be based on available safety, PK/PD and preliminary efficacy data. Patients enrolled could have different cancer types but must be confirmed with specific MAPK pathway genetic alteration (the same requirement as in phase II). The total number of patients will depend upon the number of dose expansions necessary.

Phase II Dose extension:

This is an open-label, multicenter, dose extension stage at RP2D to explore the response of patients with particular tumor types harboring MAPK genetic alteration. A maximum of 108 patients will be enrolled.

Patients enrolled will be divided into four cohorts once RP2D is defined and each of them focuses on specific tumors with specific genetic alteration, which NGS (next generation sequencing) will be used to detect, described as follows:

- **Cohort 1:** Patients with *BRAF/NRAS* (mutation sites as follows: *NRAS* G13V, *NRAS* Q61, *BRAF* V600, *BRAF* G469A, L485W, L597Q, T599dup) mutated melanoma;

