Based on [Table 10-1](#), we will perform an interim analysis for the first 23 patients. When at least 2 patients experience CR or PR or SD(SD \geq 6m) events, the study will continue recruiting up to 13 more patients in the second stage. When the total number of patients reaches the maximum sample size of 36, we reject the null hypothesis and conclude that the treatment is promising if the number of responses is greater than 3; otherwise we conclude that the treatment is not promising. An internal data review committee will use information collected from patients in the first stage to determine whether additional recruitment should be continued and if continued, whether biomarkers and/or indications need to be adjusted and whether amendment(s) to the protocol should be implemented for a better assessment of anti-tumor response.

The planned sample size for cohort 3 and cohort 4 are 9 patients and 27 patients, respectively. For detailed information on the sample size of the study, please refer to Section 10.4. of this protocol.

Figure 4-1 Study Flow Chart

[figure not shown]

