7.1.5.2 Follow-up of survival

Telephone follow-up will be conducted every 3 months since the occurrence of progressive disease or the starting of new antitumor treatment to collect patients' information on subsequent antitumor treatment and survival condition. It was completed 1 year after disease progression or initiation of new anti-tumor therapy. If patients have started new antitumor treatment after the final dose prior to end-of-treatment visit, they will directly enter the survival visit without receiving the end-of-treatment visit.

If patients terminate treatment prior to the occurrence of progressive disease, they should take part in survival follow-up to collect patients' information on subsequent antitumor treatment and survival condition.

Patients lost to follow up should be recorded as such on the CRF. For patients who are lost to follow-up, the investigator should show "due diligence" by documenting in the source documents steps taken to contact the patient, e.g., dates of telephone calls, registered letters, etc.

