10.5.2 Primary Analysis

The primary analyses in Phase I focuses on safety endpoints for HH2710 administered alone in patients with the advanced and/or refractory tumors. The RP2D will be determined based upon the observed DLTs and information from other sources (e.g. pharmacokinetics) as described in the protocol.

In Phase II, the primary analyses will investigate the preliminary efficacy of the ORR and other endpoints including DoR, DCR, TTR, TTP, PFS and 1-year OS rate for each tumor type and each genetic mutation.

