8.7.1.3 Analysis of Secondary Efficacy Endpoint

If the sample size or the number of responders allow for meaningful interpretation, Kaplan-Meier method will be used to analyze the duration of response (DoR), the progression-free survival (PFS), time to response (TTR) and time to progression (TTP) for each tumor type, genetic mutation and other factors required by sponsor. If possible, a 95% of confidence interval band should be provided for each estimate.

For all the time-to-event endpoints (DoR, PFS, TTR and TTP), the survival curve will be estimated by the Kaplan-Meier estimate, and the first percentile, the median survival, the third percentile and their 95% CI will be provided.

For Time to Response (TTR) and Duration of Response (DoR), only subjects with BOR is CR/PR during the study treatment will be calculated.

DCR and 1-year overall survival (OS) rate will be estimated and analyzed by the same methods as those in ORR.

The listing of all the time-to-event endpoints will be provided.

See Appendix , B, C and E for detailed rule of Censor date for PFS and other time-to-event endpoints.

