For the study as a whole: the end of study as a whole is defined as a minimum of 80% of patients in the Phase II stage have died, have been lost to follow-up, or have been followed for survival for minimum 12 months after the first dose of study treatment.

Treatment-emergent Adverse Event

TEAE are defined as AEs that were reported or worsened on or after the start of study drug dosing and up to the safety follow-up.

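### The pooled 80% closure rule can stop survival follow-up before month 12 for up to 21 of 108 Phase II patients, and the SAP's proportion method for 1-year OS would turn that into bias

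*Protocol*

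**What the plan says.** **Closure rule.** Protocol 4.3 opens by ending the study only when treatment, safety, disease and survival follow-up are complete for all patients. It then defines the survival part: "Completion of the survival follow-up period will occur once a minimum of 80% of patients in the Phase II stage have died". Loss to follow-up, or at least 12 months of survival follow-up from first dose, also counts. SAP Appendix E drops the other three conditions: "the end of study as a whole is defined as a minimum of 80% of patients in the Phase II stage have died", with the same two alternatives. In both documents the percentage is pooled over Phase II.

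**Per-patient follow-up.** Protocol 7.1.5.2 sets 3-monthly telephone contact from progression or new therapy and gives its end as: "It was completed 1 year after disease progression or initiation of new anti-tumor therapy".

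**Endpoint and method.** The 1-year OS rate is a Phase II secondary endpoint. Protocol 10.5.2 reports, beside ORR, "other endpoints including DoR, DCR, TTR, TTP, PFS and 1-year OS rate for each tumor type and each genetic mutation". Protocol 10.6.3 specifies Kaplan-Meier for it. SAP 8.7.1.3 differs: "DCR and 1-year overall survival (OS) rate will be estimated and analyzed by the same methods as those in ORR". SAP 8.7.1.2 gives that method as a proportion with a Clopper-Pearson interval. SAP Appendix E censors living patients, for OS, at the date last known alive. SAP 8.1 rules out imputation.

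**The concern.** A 1-year OS proportion needs each patient's vital status 12 months after first dose. The closure rule lets follow-up stop while some patients have not reached that point. These patients are not a random subset. Anyone who has died, been lost or reached month 12 already counts towards the 80%, so every unresolved patient is alive, in contact and recently enrolled. Early deaths among late enrollees are recorded, while late enrollees who are still alive have no month-12 outcome.

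The proportion method has no place for a patient whose follow-up was closed early, and the SAP does not say whether to exclude such patients or how to count them. Because the 80% is pooled while the endpoint is reported by tumor type and mutation, the shortfall can also fall unevenly, most heavily on a cohort that enrols late.

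**Working it through.** **1. The plan's own total.** Protocol 4.1: "A maximum of 108 patients will be enrolled". Cohorts 1 and 2 have a maximum of 36 each ("When the total number of patients reaches the maximum sample size of 36"). For the rest: "The planned sample size for cohort 3 and cohort 4 are 9 patients and 27 patients, respectively". The sum is 36 + 36 + 9 + 27 = 108, which reproduces the stated figure.

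**2. Patients the rule need not cover.** Formula: N − ceil(0.80 × N).

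| Phase II scenario | N | Needed | Not covered |
|---|---|---|---|
| Full enrolment | 108 | 87 (0.80 × 108 = 86.4) | 21 (19.4%) |
| One of Cohorts 1-2 stops at 23 | 95 | 76 | 19 |
| Both stop at 23 | 82 | 66 | 16 |

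**3. Loss to follow-up.** Lost patients count towards the 80%, so 21 does not cap the number with unknown 12-month status. The documents give no loss rate. If 5%, 10% or 20% of 108 are assumed lost (5, 11 or 22 patients), the maximum becomes 21 + 5 = 26, 21 + 11 = 32 or 21 + 22 = 43.

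**4. Which text governs.**
- SAP Appendix E: the 80% rule alone ends the study, so all 21 are exposed.
- Protocol 4.3: the 80% rule closes the survival component only. A patient still on treatment or in disease follow-up keeps the study open. Those exposed are alive, in survival follow-up only, and less than 12 months from first dose, so 21 is an upper bound.
- Protocol 7.1.5.2: follow-up runs to 1 year after progression or new therapy. Either event comes after first dose, so this always passes month 12. Closure at 80% contradicts it.

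**5. Effect on the estimate.** The documents give no accrual or OS figures, so these are assumptions: 108 patients entering uniformly over 12, 18, 24 or 30 months; exponential survival; a true 1-year OS of 50%; no loss. A patient is resolved at entry + min(death time, 12 months). Closure is at the 87th resolution and not before the last entry. Average estimates over the four accrual lengths:

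| Handling of unresolved patients | 1-year OS estimate |
|---|---|
| Excluded | 41-44% |
| Counted as not alive | 33-35% |
| Counted as alive | 52-55% |
| Censored, pooled Kaplan-Meier | about 50% |

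With true rates from 40% to 70%, pooled Kaplan-Meier stayed within 0.003 of the truth in all 16 scenarios. The 19.4% unresolved share is built into this model by the closure rule and is not a separate result.

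**6. Timing.** For a true rate of 50%, closure falls about 3-8 months after the last patient's first dose. Over all scenarios it falls about 2-9 months after.

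**7. A per-cohort 80%.** The numbers not covered would be 36 − 29 = 7, 36 − 29 = 7, 9 − 8 = 1 and 27 − 22 = 5, which is 20 in total. That barely changes the total but caps Cohort 3 at 1 of 9.

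**The case against.** **The Protocol already protects these patients.** Its end-of-study sentence covers all patients and all follow-up periods, and 7.1.5.2 takes each patient past month 12. This stands in part. A reader might infer that the Protocol closes the whole study at 80%, or that 21 patients can never have a known 1-year status. The Protocol does not say that; only SAP Appendix E ends the study on the 80% rule alone. What remains is a conflict between sections, with 21 as the worst case under one reading.

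**The bias comes from the estimator.** This is largely right. With closure unchanged, pooled Kaplan-Meier is close to unbiased, and SAP Appendix E does contain an OS censoring rule. The bias needs both the early closure and the SAP's proportion method. Kaplan-Meier still gives no month-12 estimate for a cohort whose living members are all censored earlier.

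**Losing all of Cohort 3 is far-fetched.** A reader might infer it because 9 is less than 21. Under the uniform-accrual model its probability is C(21,9)/C(108,9), about 7.5 × 10⁻⁸. It would require Cohort 3 to enrol almost entirely last, with all nine alive and in contact at closure. No document describes such accrual, so it is only a theoretical bound. The lack of a per-cohort minimum remains a fair point.

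**Little depends on it.** The 1-year OS rate is one of several secondary endpoints in a study described as descriptive, and no decision rule uses it. Protocol 4.3 accepts incomplete survival follow-up if enrolment stops early, and SAP section 7 records early termination. This stands and lowers the priority.

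**Conclusion.** The concern holds in a limited form. The pooled 80% rule in Protocol 4.3 and SAP Appendix E does not fit the all-patients sentence in 4.3 or the follow-up in 7.1.5.2. At full enrolment up to 21 of 108 patients could be cut off alive before month 12; the number is smaller under the Protocol if treatment or disease follow-up keeps the study open. Losses to follow-up add to those with unknown status.

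Combined with the SAP's proportion method, this would bias the 1-year OS rate by roughly 6-9 points downward (unresolved patients excluded), 15-17 points downward (counted as not alive) or 2-5 points upward (counted as alive), against a true 50%. These sizes rest on the assumed accrual and survival pattern. The count of 21 rests only on the plan's own numbers. This is a flaw in the plan as written; given the early termination, the analysis is unlikely to be run at 108 patients.

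**What to change.** 1. Reconcile Protocol 4.3, Protocol 7.1.5.2 and the end-of-study definition in SAP Appendix E. Survival follow-up should close only when every treated Phase II patient has died, withdrawn consent, been documented as lost, or been followed for at least 12 months from first dose.
2. If a percentage is kept for operational reasons, apply it within each cohort and make a month-12 vital-status call for each remaining patient.
3. Take the data cut for the 1-year OS rate at or after that point.
4. In SAP 8.7.1.3, estimate the 1-year OS rate by Kaplan-Meier, as in Protocol 10.6.3, with the OS censoring rule already in SAP Appendix E. This also handles patients who are lost or withdraw, whom the first change alone would leave without a rule.

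**Cost.** A few sentences across the two documents. The study would close about 3-10 months later under the assumptions above, and at most 12. At most about 21 patients would need the 3-monthly telephone contacts already scheduled. No new patients, visits or procedures are needed.

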4.4 Early study termination

The study can be terminated at any time for any reason (such as safety or efficacy) by Haihe.

Should this be necessary, the patient should be seen as soon as possible and the same assessments should be performed as described in [Section 7.1.4.1](#) for a prematurely withdrawn patient. The investigator may be informed of additional procedures to be followed in order to ensure that adequate consideration is given to the protection of the patient's interests. The investigator will be responsible for informing Institutional Review Boards (IRBs) and/or ethics committees (ECs) of the early termination of the study.

5 Population

5.1 Patient population

The investigator or designee must ensure that only patients who meet all the following inclusion and none of the exclusion criteria are offered treatment in the study.

Phase I

For the dose escalation stage, patients who have been diagnosed with histologically or cytologically documented, unresectable/metastatic tumors that are refractory or intolerant to standard therapy or for whom no curative standard therapy exists.

- For LCH/ECD: Eligible patients must have multifocal disease and the diagnosis must be confirmed by pathological evaluation of the affected tissue.

For the dose expansion stage, patients must have been diagnosed with histologically or cytologically documented, unresectable/metastatic tumors harboring MAPK pathway genetic alterations. Patients with a BRAF V600 mutation must have progressed on or after standard therapy, including BRAF and/or MEK inhibitors (≤ 3 lines).

Phase II

Patients must have been diagnosed with histologically or cytologically documented, unresectable/metastatic tumors harboring MAPK pathway genetic alterations. Patients with a BRAF V600 mutation must have progressed on or after standard therapy, including BRAF and/or MEK inhibitors (≤ 3 lines). Patients will be enrolled in Cohorts 1-4 depending upon their tumor type.

In some cases, re-screening is allowed, details refer to [Section 7.1.2](#).

5.2 Inclusion criteria

Patients eligible for inclusion in this study must meet all of the following criteria:

1. Provide signed and dated informed consent prior to initiation of any study-related procedures;
2. Male or female patients aged ≥ 18 years;
3. Phase I dose escalation stage: Patients who have been diagnosed with histologically or cytological documented, unresectable/metastatic tumors that are refractory or intolerant to standard therapy or for whom no curative standard therapy exists.
 - For LCH/ECD: Eligible patients must have multifocal disease and the diagnosis must be confirmed by pathological evaluation of the affected tissue.
4. For Phase I expansion stage and Phase II stage: Histologically or cytologically documented unresectable/metastatic tumors with evidence of genetic mutations affecting MAPK

pathway is required. Patients with a BRAF V600 mutation must have progressed on or after standard therapy, including BRAF and/or MEK inhibitors (≤ 3 lines). Patients entering the Phase 2 portion of the trial will be enrolled in Cohorts 1-4 depending upon their tumor types.

- Cohort 1: Patients with *BRAF/NRAS* (mutation sites including: *NRAS G13V, NRAS Q61, BRAF V600, BRAF G469A, L485W, L597Q, T599dup*) mutated melanoma;
- Cohort 2: Patients with *BRAF/NRAS* (mutation sites including: *NRAS G13V, NRAS Q61, BRAF V600, BRAF G469A, L485W, L597Q, T599dup*) mutated non-small cell lung cancer;
- Cohort 3: Patients with *BRAF V600* mutated Langerhans Cell Histiocytosis Syndrome (LCH)/ Erdheim-Chester disease (ECD);
 - For LCH/ECD: Eligible patients must have multifocal disease and the diagnosis must be confirmed by pathological evaluation of the affected tissue.
- Cohort 4: Patients with *RAS/RAF/MEK/ERK* mutated tumor types that are not included in other cohorts.

5. Patients in the Phase I dose escalation portion of the trial may have measurable (per RECIST v1.1) or evaluable disease. Patients in the Phase I dose expansion and Phase II portions of the trial must have measurable disease per RECIST v1.1.

6. Eastern Cooperative Oncology Group (ECOG) performance status ≤ 1 .

7. Predicted life expectancy ≥ 3 months;

8. Adequate renal function defined as a creatinine clearance ≥ 60 mL/min (using Cockcroft-Gault formula, see [Appendix 14.3](#));

9. Adequate hepatic function [total bilirubin $\leq 1.5 \times$ UNL; AST (aspartate aminotransferase) and ALT (alanine aminotransferase) $\leq 3 \times$ UNL or $\leq 5 \times$ UNL if due to liver involvement by tumor];

10. Adequate cardiac function, $>$ institutional lower limit of normal e.g., left ventricular ejection fraction (LVEF) of $\geq 50\%$ as assessed by ultrasound/echocardiography (ECHO) or multi-gated acquisition (MUGA); corrected QT interval (QTcF) < 460 ms (male patients), < 470 ms (female patients) (using QTc Fridericia's formula. See [Appendix 14.6](#));

11. Adequate bone marrow function : patients must not have required blood transfusion or growth factor support ≤ 7 days before sample collection for the following : ,

- absolute neutrophil count $\geq 1.5 \times 10^9/L$;
- hemoglobin ≥ 9 g/dL;

- platelet count $\geq 100 \times 10^9/L$;
- International normalized ratio (INR) ≤ 1.5 ;
- activated partial prothrombin time (APTT) $\leq 1.5 \times ULN$;

12. Willing and able to participate in the trial and comply with all trial requirements;

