After conscious Beagle dogs were given a single dose of HH2710 (5, 20 and 100 mg/kg) via oral gavage, increased heart rate (HR), decreased PR interval and decreased QT interval without changes in corrected QT (QTcR) in both genders, decreased of systolic blood pressure (SBP), diastolic blood pressure (DBP) and mean blood pressure (MBP) in the males and decreased of SBP in the females were found at 100 mg/kg. All these changes were resolved within the observation period. And a slightly decreased of body temperature was temporarily noted at 3 hrs post-dose in the males of 100 and 20 mg/kg groups. No test article-related arrhythmia was observed in all animals.

In Ames test, HH2710 is not mutagenic to *Salmonella typhimurium*. In chromosomal aberration test, HH2710 did not induce chromosome aberrations in cultured CHL cells. In bone marrow

micronucleus test, HH2710 could not induce an increase in the micronucleated polychromatic erythrocyte of rat bone marrow.

In the human ether-a-go-go-related gene (hERG) study, in human embryonic kidney cell lines (hERG-HEK293) steadily expressing hERG channels, the hERG current inhibition rate by HH2710 at 0.3, 1, 3, 10 and 30 $\mu\text{mol/L}$ was 1.1%, 6.9%, 17.8%, 41.1% and 73.2%, respectively; and the IC_{50} value was 12.8 $\mu\text{mol/L}$.

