	ALT/AST > 3 ULN and concomitant TBL > 2 ULN in the absence of evidence of biliary obstruction (i.e., significant elevation of ALP) or some other explanation of the injury (e.g., viral hepatitis, alcohol hepatitis) of any duration (i.e. Hy's law)
	AST or ALT CTCAE Grade 3 for > 72 hours
	AST or ALT CTCAE Grade 4
	Serum alkaline phosphatase CTCAE Grade 3
	Serum lipase and/or serum amylase (asymptomatic) CTCAE Grade 3 > 72 hours
	Serum lipase and/or serum amylase CTCAE Grade 4
	Serum creatinine CTCAE Grade ≥ 3
	Serum CK/CPK CTCAE Grade 3 for > 72 hours
	Serum CK/CPK CTCAE Grade 4
	Neutrophil count CTCAE Grade 3 for > 72 hours
	Neutrophil count CTCAE Grade 4
	Platelet count CTCAE Grade 3 with signs of bleeding
	Platelet count CTCAE Grade 4
	ECG QTc interval prolonged CTCAE \geq Grade 3
	Electrolyte imbalance Grade 4; Asymptomatic electrolyte imbalance Grade 3 > 72 hours
Other hematologic & non-hematologic toxicities	Any other CTCAE Grade ≥ 3 toxicity except: Lymphocyte count decreased (lymphopenia) CTCAE Grade ≥ 3 unless clinically significant
	Other clinically significant/unacceptable toxic events not listed, judged by the SMC as DLT;

TOXICITY	DLT CRITERIA
All AEs of the specified grade and toxicity must be considered a DLT if they cannot definitively be attributed to disease progression or other extraneous cause.	

^a For any CTCAE Grade 3 or 4 hepatic toxicity that does not resolve within 7 days to CTCAE Grade ≤ 1 (or CTCAE Grade ≤ 2 if liver infiltration with tumor present), an abdominal CT scan must be performed to assess if it is related to disease progression.
	

CTCAE V5.0 will be used for all grading.
	

Patients may receive supportive care (e.g. Packed red blood cells) as per local institutional guidelines.
	

G-CSF may be used to treat patients who have developed dose-limiting neutropenia, as per institutional guidelines, following discontinuation of HH2710 treatment. Optimal therapy for vomiting or diarrhea will be based in institutional guidelines, with consideration of the prohibited medications listed in this protocol. Grade 3 laboratory investigations other than serum creatinine, bilirubin, AST or ALT will not be considered a DLT unless they are associated with clinical manifestations and judged by the SMC.
	

For the exceptions provided, the Grade 3 AEs should resolve to \leq Grade 1 within 72 hours
	

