Grade 3 (>2.0 - 5.0 x ULN with signs or symptoms; >5.0 x ULN and asymptomatic)	Discontinue dose of until resolved to Grade \leq 2, then: 
 - If resolved in \leq 7 days, then maintain dose level - If resolved in > 7 days, then \downarrow 1 dose level
Grade 4 (>5.0 x ULN and with signs or symptoms)	Permanently discontinue HH2710.
Cardiac general	
Grade 1 or 2	Maintain dose level
Grade 3	Discontinue dose until resolved to \leq Grade 1, then \downarrow 1 dose level
Grade 4	Discontinue dose and discontinue patient from study drug treatment

Recommended dose modifications for HH2710	
Worst toxicity CTCAE Grade^a (value)	Recommended dose modifications any time during a cycle of therapy, including intended day of dosing^b
Electrocardiogram QT corrected (QTc) interval prolonged	
Grade 1 or 2 Heart Failure	Maintain dose level
Grade 3 Heart Failure	Permanently discontinue HH2710 and discontinue patient from study drug treatment
Grade 4 Heart Failure	Permanently discontinue HH2710 and discontinue patient from study drug treatment
Grade 2 Ejection Fraction (EF) Decreased (resting EF: 50-40%; or 10-19% drop from baseline)	Discontinue HH2710 until ejection fraction returns to a value greater than the institutional lower limit of normal and the absolute decrease from baseline is $\leq 15\%$, then maintain dose level.
Grade 3-4 EF Decreased (resting EF 39-20%; or $\geq 20\%$ drop from baseline)	Permanently discontinue HH2710
Grade 1 and 2 (QTcF 450-500ms)	Maintain dose level
Grade 3 (QTcF ≥ 501 ms on at least two separate ECGs)	Discontinue dose until resolved to Grade ≤ 2 , then: 
 - If resolved in ≤ 7 days, then maintain dose level - If resolved in > 7 days, then $\downarrow 1$ dose level
Grade 4 (QTcF ≥ 501 ms or > 60 ms change from baseline and Torsades de pointes or polymorphic ventricular tachycardia or signs/symptoms of serious)	Permanently discontinue HH2710
Eye disorders	
Retinal vein occlusion (RVO)	Permanently discontinue HH2710.

Recommended dose modifications for HH2710	
Worst toxicity CTCAE Grade^a (value)	Recommended dose modifications any time during a cycle of therapy, including intended day of dosing^b
Other Grade 1 or 2 eye AEs	Discontinue dose until resolved to baseline, HH2710 could be restarted after assessed by ophthalmologist and investigator, maintain dose level or one dose level reduced as clinically indicated.

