7.2.1.6 Echocardiogram or MUGA (multiple gated acquisition) scan

Left ventricular ejection fraction (LVEF) should be measured at screening, at the investigator's discretion if there are signs or symptoms of cardiotoxicity during the study, and at the SFUV.

LVEF can be measured via echocardiogram or MUGA scan. A delegated qualified staff should be responsible for LVEF measurement. LVEF must be within normal range.

7.2.1.7 12-lead Electrocardiogram

A standard 12-lead ECG will take place on screening and subsequent visits. Patients should be supine for 5 minutes prior to the ECG. ECGs will be obtained prior to dosing(-60min), one hour post-dose(\pm 20min), three hours post-dose(\pm 30min), four hours post-dose(\pm 30min), and eight hours post-dose(\pm 60min) on Cycle 1 Day 1 and Cycle 2 Day 1. ECG measurement timepoints will

match PK sampling timepoints, ECG measurement must be taken within 15 min before PK sampling at each time points. The timepoints may be modified when the PK data (HH2710 and selected metabolites) in humans is available.

Standard ECG parameters, including heart rate, QRS, PR, RR, QT, and the QT interval corrected for heart rate using Frederica's formula will be measured.

ECG trace report will be collected and archived at patient chart and study file respectively.

Interpretation of the tracing must be made by a qualified physician and documented on the ECG CRF page. Each ECG tracing should be labeled with the study number, patient initials (where regulations permit), patient number, date, and kept in the source documents at the study site. Clinically significant abnormalities present when the patient signed informed consent should be reported on the Medical History CRF page. Clinically significant findings must be discussed with Haihe prior to enrolling the patient in the study. New or worsened clinically significant findings occurring after informed consent must be recorded on the Adverse Events CRF page.

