14.6 Appendix 6 QTc Fridericia's formula

$$QTcF = \frac{QT}{\sqrt[4]{RR}}$$

QT refers to the interval from the start of the Q wave to the end of the T wave.

RR refers to the interval from the occurrence of QRS wave group to the occurrence of the next QRS wave.

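### Appendix 14.6, which inclusion criterion 10 cites for QTcF, carries Fridericia's name but appears to print a fourth root of RR, so QTcF is understated above 60 bpm wherever that equation is used

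*Protocol*

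**What the plan says.** Protocol Section 5.2, criterion 10 (repeated in the protocol summary), sets the eligibility limits as "corrected QT interval (QTcF) < 460 ms (male patients), < 470 ms (female patients". It names the method, "using QTc Fridericia's formula. See", and the reference that follows is to Appendix 14.6.

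Appendix 14.6 has Fridericia's name in its title. Its equation, as the text reads, is QT divided by the fourth root of RR. It explains that "RR refers to the interval from the occurrence of QRS wave group to the occurrence of the next QRS wave" and does not say whether RR is in seconds or milliseconds.

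QTc is used in four other places, none of which cites the appendix:

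- Table 6-8 (Section 6.3.1) defines its Grade 3 row by a QTcF of at least "501 ms on at least two separate ECGs". The Grade 4 row also uses QTcF.
- Table 6-6 (Section 6.2.4) has a DLT row, "ECG QTc interval prolonged CTCAE" Grade 3 or above, which says QTc and names no correction.
- Section 7.2.1.7 says that "the QT interval corrected for heart rate using Frederica's formula will be measured".
- SAP Section 8.8.1.6 lists QTcF among the ECG parameters and gives no derivation.

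The protocol's abbreviation list defines QTcF as the Fridericia-corrected interval.

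**The concern.** The named method and the printed equation disagree. Inclusion 10 relies on this equation for a numerical safety limit. A site that calculates QTcF by hand, or a programmer who derives it for the ECG tables, has no other written formula to follow in either document.

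The error also varies with heart rate. A fourth root corrects less than a cube root, so above 60 bpm the printed equation gives a lower QTcF than Fridericia's formula, by a margin that widens as the rate rises. That is the less cautious direction for a limit on QT prolongation. Below 60 bpm the error reverses. Values from patients or visits with different heart rates would therefore not be on a common scale, which also affects the change-from-baseline summaries planned in SAP Section 8.8.1.6.

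**Working it through.** The plan gives no worked QTc value, so there is no stated figure to reproduce. The check compares the two formulas directly.

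**Inputs**
- Limits of 460 and 470 ms: inclusion 10.
- Limit of 501 ms: Table 6-8.
- Printed equation, QT / RR^(1/4): Appendix 14.6.
- Fridericia's correction, QT / RR^(1/3): the definition of the named method.
- RR = 60 / heart rate, in seconds. The unit is an assumption because the appendix states none. Milliseconds would not give a usable number: QT 400 ms with RR 600 ms gives 400 / 600^(1/4) = 400 / 4.95, or about 81 ms.
- Heart rates of 50 to 120 bpm: an illustrative range, because the documents report no patient heart rates.

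**Ratio of the two formulas**

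Printed / cube-root = RR^(1/3) / RR^(1/4) = RR^(1/3 − 1/4) = RR^(1/12).

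The last three columns show the cube-root QTcF when the printed equation reads exactly at a limit, that is, the limit divided by the ratio.

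| Heart rate (bpm) | RR (s) | Ratio | At 460 ms | At 470 ms | At 501 ms |
|---|---|---|---|---|---|
| 50 | 1.200 | 1.0153 | 453.1 | 462.9 | 493.4 |
| 60 | 1.000 | 1.0000 | 460.0 | 470.0 | 501.0 |
| 70 | 0.857 | 0.9872 | 465.9 | 476.1 | 507.5 |
| 80 | 0.750 | 0.9763 | 471.2 | 481.4 | 513.2 |
| 90 | 0.667 | 0.9668 | 475.8 | 486.2 | 518.2 |
| 100 | 0.600 | 0.9583 | 480.0 | 490.4 | 522.8 |
| 120 | 0.500 | 0.9439 | 487.4 | 497.9 | 530.8 |

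The understatement is therefore 1.3% at 70 bpm, 2.4% at 80, 3.3% at 90, 4.2% at 100 and 5.6% at 120. At 50 bpm the printed equation overstates by 1.5%.

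**A single ECG**

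Take QT 400 ms at 100 bpm, so RR = 0.6 s.
- Printed: 400 / 0.6^(1/4) = 400 / 0.8801 = 454.5 ms, which meets both eligibility limits.
- Cube root: 400 / 0.6^(1/3) = 400 / 0.8434 = 474.3 ms, which meets neither.

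**How far the equation reaches**

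Only inclusion 10 cites Appendix 14.6. Table 6-8, Section 7.2.1.7 and SAP Section 8.8.1.6 are linked to it by the name QTcF or Fridericia alone. The Table 6-6 row is affected only if its QTc is meant as QTcF.

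**The case against.** The point depends on one small root index in text read from a PDF, and small symbols elsewhere in that text are damaged. In Table 6-5, for example, nearly every number carries a stray superscript. A printed 3 could have been read as a 4. The amendment log records an earlier edit to this appendix but does not say what changed, so it does not settle the matter. This objection stands as a reason to look at the PDF first. Against it, the index is explicit rather than garbled, it contradicts the appendix's own title, and no other section corrects it.

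Three stronger readings are tempting, and the documents do not support them.

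- A reader might infer that the eligibility, DLT and dose-hold limits all refer to this equation. Only inclusion 10 does.
- A reader might infer that ineligible patients were admitted or Grade 3 events missed. That requires QTcF to have been calculated from the appendix. Section 7.2.1.7 treats it as a standard measured ECG parameter and has a qualified physician interpret the tracing. An ECG machine that already applies the cube root would make the appendix irrelevant to the recorded values. The documents do not say which source was used.
- A reader might infer that a heart-rate effect of HH2710 would lower the computed QTcF and so hide prolongation. Protocol Section 1.2.1.1.3 does report "increased heart rate (HR), decreased PR interval and decreased QT interval" in dogs at 100 mg/kg, but with unchanged QTcR and with resolution during the observation period. Section 1.2.2 reports no significant cardiotoxicity in clinical data so far. Nor does the printed value fall as heart rate rises at a fixed QT: with QT 400 ms it goes from 400 ms at 60 bpm to 454.5 ms at 100 bpm. It is low only relative to the cube-root result.

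It is also fair to say that SAP Section 7 reports the program stopped and the study ended early. What remains is mainly the reporting of QTcF for patients already treated, 26 of whom had been enrolled by 18 January 2022.

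**Conclusion.** The point holds as a defect in a stated safety formula. As the text reads, Appendix 14.6 gives an equation that is not the one in its title, states no unit for RR, and is the method that inclusion 10 cites. Where that equation is used with RR in seconds, QTcF is understated by about 1% to 4% between 70 and 100 bpm. Readings at the 460/470 ms limits then correspond to cube-root values about 11 ms higher at 80 bpm and 20 ms higher at 100 bpm.

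This rests on three assumptions: that the PDF really prints a 4, that RR is in seconds, and that someone computed QTcF from the appendix. The first takes a minute to check. The third is unknown, so no effect on enrolment, DLT classification or dose holding has been shown. Even if the PDF prints a cube root, the missing RR unit and the unnamed correction in the Table 6-6 row still need attention.

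**What to change.** 1. Check the root index in Appendix 14.6 against the source PDF.
2. If it is a fourth root, correct the appendix to QTcF = QT / RR^(1/3). In either case state that RR is in seconds.
3. Cite that one formula in inclusion 10, Table 6-6, Table 6-8, Section 7.2.1.7 and SAP Section 8.8.1.6, and say in the Table 6-6 row whether QTc means QTcF. The thresholds stay as they are.
4. Establish how the recorded QTcF values were produced. Where they came from the appendix equation, derive QTcF for SAP Section 8.8.1.6 from the QT and RR collected under Section 7.2.1.7.

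The cost is one corrected equation, a few cross-references, a query to sites about the source of QTcF, and at most one derivation in the ECG programming. Some stored values may change. No new data are needed.
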